#### B. Study Participants:

It is anticipated that the study will screen 100 individuals in order to complete a total of up to 75 participants. We will recruit male and female participants who satisfy the inclusion and exclusion criteria outlined in the following sections.

Potential participants will be recruited predominantly through media advertisements (ex. local newspapers, flyers), institutional postings, market research firms, word of mouth,

<sup>2 Internal Philips Interim Report- Data on File

or existing site databases of individuals who may have previously indicated an interest in participating in research.

### Inclusion Criteria

- Able to provide written informed consent prior to admission
- Able to read, write and speak English
- Adult volunteers aged 21-50 years
- Working full time with a regular work schedule; Full time is considered 4- 10 hour days or 5- 8 hour days with a start time of 7am or later
- Self-reported regular sleep schedule who are able to maintain their sleep schedule during the course of the study
- Self-reported sleep duration of > 5hrs. and ≤ 7 hrs. +/- 15 minutes (verified by 6 work days of ambulatory sleep monitoring with wrist actigraphy and daily logs)
- Self-reported sleep latency > 30 minutes no more than once / wk. (time to fall asleep)
- Self-reported wake time after sleep onset ≤ 30 minutes
- Participants who regularly use an alarm clock during the work week and who **self-report**:
  - i. Regular time in bed (TIB) on work days of  $\leq$ 7 hours
  - Regular increase in sleep duration by ≥ 1 hour during non-work days as compared to work days, either by nocturnal bedtime extension of via a daytime nap

# Exclusion Criteria:

- Participation in another interventional study in the past 30 days.
- Previously enrolled in a PowerSleep study.
- Major controlled\* or uncontrolled medical condition such as congestive heart failure, neuromuscular disease, renal failure, cancer, COPD, respiratory failure or insufficiency, or patients requiring oxygen therapy (as determined by self-report and reviewed by the study PI.)
- Currently working night, swing, split or rotating shift.
- Current use or use of within the past month of a prescription or over-the-counter sleep medication or stimulant; use of psychoactive medication (based on self-report and review with a study clinician). Refer to table below for examples.
- Pregnant or currently breast feeding
- Current Smokers or using nicotine replacement therapy. Those that have been nicotine free for 30 days will be included.
- Body Mass Index > 40 kg/m^2
- Prior diagnosis of any sleep disorder including
  - a. Obstructive Sleep Apnea (AHI ≥15 events/hour) from ambulatory or in lab polysomnography
  - b. Restless legs syndrome, or periodic limb movement disorder

- c. Insomnia
- d. Parasomnia
- High Risk of OSA based on STOP-BANG Questionnaire ("yes" on at least 4 of 8 questions)
- High Risk of Restless Legs Syndrome (RLS) based on Cambridge-Hopkins Screening questionnaire
- High Risk of Insomnia based on Insomnia Severity Index (score of 22 or higher)
- Self-reported history of excessive alcohol intake- self-report 
   > 21 drinks / wk or binge alcohol consumption ( >5 drinks per day)
- Excessive caffeine consumption (> 650mg/day combining all caffeinated drinks regularly absorbed during workdays.) Caffeine intake must be regular and maintained throughout study and on testing days
- Individuals who self-report a history of recurrent seizures or epilepsy or have a history of medical conditions that could increase the chance of seizures (e.g. stroke, aneurysm, brain surgery, structural brain lesion).
- Individuals who self-report severe contact dermatitis or allergy to silicone, nickel or silver.
- Individuals who self-report moderate hearing loss.
- Inability to achieve appropriate headband fit.
- Planned travel across more than one time zone one month prior to and or during the anticipated period of the study with PowerSleep device use
- Intentional naps during the work week.
- Alpha-Delta waveforms as determined by Baseline night PowerSleep Device data collection

\*Participants who are on a stable and well-tolerated pharmacological treatment for hypertension, dyslipidemia, or thyroid replacement will not be excluded as long as they continue to take their medication at the same dose and at the same time(s) of day.

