# C. Study Procedures and Measurements:

Participants may be pre-screened over the phone by the site or a market research firm to determine eligibility. A screening script will include a general review of key inclusion and exclusion criteria, the STOP-BANG questionnaire to assess the risk / possibility of an undiagnosed sleep disorder [46] and other questionnaires. Participants that meet all eligibility criteria will be asked to come into the office for a screening daytime visit (Visit 1) involving a detailed presentation of the study (informed consent) and an interview to verify eligibility and work schedules.

Participants who are interested and eligible will be consented. Participants will scheduled for a second daytime visit, 5 overnight lab visits, and provided with information on use of the actigraph. At Daytime Visit 2, participant qualification will be assessed based on the PowerSleep device data, actigraphy, and sleep logs. Qualifying participants will be randomized and scheduled for their sleep lab visits.

Participants will use the PowerSleep device within the active and sham study arm for two nights each week. After completing a baseline night in the lab, participants will sleep in the sleep lab two consecutive nights for two consecutive weeks. The first week participants will be randomized to active or sham and complete two consecutive nights. Participants will be asked to come in the same nights the following week to cross-over to the other arm of the study.

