### Overnight in-lab visit 3 (Work Week 1) followed by Daytime in-lab testing (8

**hours)**: On the next evening participants will be asked to return to the sleep lab for the second study arm night. Participants will be asked to report to the lab up to 4 hours before bedtime. Participant will be asked to complete the PAL learning activity prior to bedtime (120 to 30 minutes before lights out). Participants will be asked to go to bed and awaken at the same time as their regular work-night sleep schedule. Participants will be asked to wear the PowerSleep device and PSG electrodes during this overnight visit.

On the morning of the day following the overnight in lab visit work week 1, participants will remain in the lab and undergo the following assessments:

After Wake-Up

• Collect and download PowerSleep device data

Anytime after wake-up

- Review of any reported changes in medical condition since last visit
- Collect sleep logs
- Data download from actigraph
- Questionnaire identifying whether participant believes they had undergone active versus sham treatment
- Breakfast- participants can have one (1) 6 ounce cup of coffee or caffeine equivalent. Coffee or equivalent is only for those who routinely drink caffeine in the morning.
- Lunch

1 hour after wake up:

- Complete morning recall of PAL task
- Complete 3 minute PVT
- VAS for sleep quality
- Verbal fluency

- Karolinska Sleepiness Scale
- Samn-Perelli Fatigue Scale

2 hours after wake up:

- 4- Research Multiple Sleep Latency Test (see Appendix II for standardized MSLT procedures) each nap is followed by the following assessments:
  - Complete a 3 minute PVT
  - VAS for mood and vigor
  - Karolinska Sleepiness Scale
  - o Samn-Perelli Fatigue Scale
- •

Participants will continue to wear the actigraph and complete sleep logs until the next set of overnight visits.

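### The optional breakfast coffee on testing days has no fixed time, so it can fall before the daytime tests in one week and after or between them in the other

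*Combined protocol and SAP*

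**What the plan says.** **Eligibility.** The Exclusion Criteria in III.B rule out "Excessive caffeine consumption (> 650mg/day combining all caffeinated drinks regularly absorbed during workdays". The same bullet adds: "Caffeine intake must be regular and maintained throughout study and on testing days". The footnote to that list admits people on certain stable medicines provided they "continue to take their medication at the same dose and at the same time(s) of day".

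**Visit schedule.** Under III.C, participants are asked to "come in the same nights the following week to cross-over". On every lab night, bedtime and wake time follow the regular work-night schedule.

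**Testing days.** The procedures after overnight visits 3 and 5 carry the same wording. Under the heading "Anytime after wake-up" they list: "Breakfast- participants can have one (1) 6 ounce cup of coffee or caffeine equivalent". A restriction follows: "Coffee or equivalent is only for those who routinely drink caffeine in the morning". Lunch is in the same list, with nothing said about caffeine.

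**Test times.** The 1-hour list begins with "Complete morning recall of PAL task" and continues with the PVT, the sleep-quality VAS, verbal fluency, the KSS and Samn-Perelli. From 2 hours after waking there are four MSLT naps, each followed by the PVT, the mood and vigor VAS, the KSS and Samn-Perelli. Appendix II holds the MSLT start to within 5 minutes and spaces the naps about two hours apart.

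**Analysis.** The Secondary Efficacy Analysis applies the SWA model to the daytime outcomes, that is, a paired t-test or Wilcoxon signed-rank test of active against sham.

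**The concern.** Caffeine acts on alertness, and alertness is what most of the daytime outcomes measure. The tests are tied to waking time, but the cup is not. It is also optional, and no record of its amount or time is required.

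Each participant is compared with himself or herself across two weeks. A cup whose timing differs between those weeks enters the difference directly and widens its spread. The exposed outcomes are MSLT latency, the PVT, the sleepiness and fatigue scales, the two VAS measures, PAL recall and verbal fluency. The first secondary aim rests on them. The second secondary aim, which relates daytime changes to SWA changes, uses the same differences. Without a record, the variation could not be examined afterwards.

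**Working it through.** The plan gives no figure on this point, so there is nothing to reproduce. The check compares the text and then illustrates the size.

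**1. Where the cup can fall.** The battery is at 1 hour. The naps start at about 2, 2 + 2 = 4, 4 + 2 = 6 and 6 + 2 = 8 hours after waking. A cup in the first hour precedes everything. A cup between 1 and 2 hours follows the battery but precedes the first nap. A cup after 2 hours falls between naps. The heading on the breakfast line allows all three, and nothing requires the same one in both weeks.

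**2. What the existing rules settle.**

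| Feature of the cup | Settled by the text? |
|---|---|
| Upper limit at breakfast | Yes, one cup, same wording in both weeks |
| Same choice and amount in both weeks | In substance, through the rule that intake be regular and maintained |
| Same time after waking in both weeks | No |
| Amount and time recorded | No |
| Caffeine after breakfast | Not addressed |

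Appendix I, which the Baseline Night section cites for restrictions on participant activities, contains no caffeine rule. Neither does Appendix II.

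**3. Do the two caffeine rules contradict each other?** The documents give no caffeine content per cup. At an assumed 60 to 150 mg per 6-ounce cup, the daily ceiling equals 650/150 = 4.3 to 650/60 = 10.8 cups, so people who usually take several cups are eligible. However, the ceiling is stated per day, the one-cup limit applies to breakfast, and no text bars caffeine later. A usual two-cup morning drinker could keep the daily total by taking the second cup after breakfast. Which rule has precedence is unclear, but the two are not strictly contradictory. The limit is also the same in both weeks, so by itself it creates no between-week difference.

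**4. Size of the noise.** Inputs: 50 complete data sets (Determination of Sample Size); a fraction f of participants whose cup varies between weeks (assumed); an added between-week SD of r times the SD of the paired difference (assumed, and taken as independent of other variation). The average variance is multiplied by 1 + f r², so for a paired t-test:

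effective n = 50 / (1 + f r²)

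| r | f = 0.25 | f = 0.5 | f = 1 |
|---|---|---|---|
| 0.1 | 49.9 | 49.8 | 49.5 |
| 0.2 | 49.5 | 49.0 | 48.1 |
| 0.3 | 48.9 | 47.8 | 45.9 |

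The loss runs from 50 − 49.9 = 0.1 to 50 − 45.9 = 4.1 data sets. The standard error rises by √(1 + 0.25 × 0.01) − 1, about 0.1%, at the low corner and by √1.09 − 1, about 4.4%, at the high corner.

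**5. Primary endpoint.** SWA comes from the two nights of each week. The testing-day breakfast follows the second of those nights, so that cup cannot change the SWA of the same week.

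**The case against.** The strongest reply is that ordinary practice already covers most of this. A site would follow the specific visit instruction over a general eligibility bullet. The rule to keep intake regular already discourages taking the cup in one week and skipping it in the other. Wake times are regular, the nights match across weeks, the tests are anchored to waking, order is randomized, and participants and staff are blinded. The medication footnote is an eligibility condition, not a rule for standardizing measurements. Even the extreme corner of the illustration costs little, and the protocol states no power target for daytime outcomes. The figure of 50 is discussed there for SWA.

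Most of that stands. What it leaves open is the time of the cup and any record of it. The footnote is useful only as a model for the wording.

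Two stronger readings are tempting. A reader might infer that the maintain rule and the one-cup limit cannot both be obeyed by anyone who usually has more than one morning cup. That requires reading the maintain rule as fixing the morning pattern, or the breakfast cup as the day's only caffeine, and the text says neither. A reader might also infer a biased treatment comparison, for instance if sleepier participants take the cup sooner. The documents say nothing about when participants take it, the wording is the same in both weeks, and order is randomized, so no bias is shown. Nor does the number of daytime assessments measure importance: it reflects the length of the schedule, and many participants may not be affected.

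**Conclusion.** The point holds as a small, cheap improvement. The plan leaves the time of the testing-morning cup open while fixing the times of the tests that caffeine could influence. This admits avoidable within-person noise in the paired daytime secondary outcomes.

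The share of participants affected is unknown, because the documents give no distribution of caffeine intake or timing. The loss of 0.1 to 4.1 out of 50 data sets rests wholly on the assumed f and r, and it bears on precision only. Participants who take no morning caffeine, or who take one cup at a steady time, are unaffected. The precedence of the two caffeine rules and the silence on later caffeine call for clarification only.

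**What to change.** In the testing-day procedures after visits 3 and 5, move the cup out of the open-timed list. Require each participant to take the same amount, none or one cup, at the same set time after waking on both testing days, before the 1-hour battery. Allow no further caffeine until the last nap is complete. The same-dose, same-time wording of the medication footnote can serve as the model. Add one source-document field for amount and time. In the Exclusion Criteria, note that this allowance governs on testing days.

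The cost is a few sentences of protocol text and one field. The downside is that heavier users are tested below their usual caffeine, equally under active and sham. The breakfast limit already points that way, but the bar on later caffeine is new and should be explained to participants. If the change is made during enrollment, apply it only to participants who have not yet had their first testing day, so that nobody's two weeks fall under different rules.

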# Concomitant Medications:

The Investigator will make all final decisions regarding exclusion of participants on the basis of medication.

Class	Examples	
Sedating Antihistamines	chlorpheniramine, brompheniramine,	
	diphenhydramine, doxylamine	
OTC Decongestants	phenylephrine, ephedrine,	
	pseudoephedrine	
Sedative/Hypnotics	zolpidem, eszopiclone, zaleplon,	
	ramelteon, triazolam, gabitril, tiagabine,	

Classes of medications that will not be allowed include:

	suvorexant, gamma-hydroxybutyrate,	
	tasimelteon	
Anxiolytics	alprazolam, clonazepam, diazepam,	
	lorazepam	
Sedating Antidepressants	amitriptyline, nortriptyline, duloxetine,	
	venlafaxine, mirtazapine, nefazodone,	
	buspirone,	
Medications for Attention Deficit	atomoxetine, methylphenidate,	
Hyperactivity Disorder	amphetamine	
Stimulants	amphetamine, modafinil, armodafinil	
Dopamine Agonists	ropinirole, pramipexole, rotigotine	
Narcotic/Opioid Analgesics	Including tramadol	
Dextromethorphan	Many OTC cough products	
Dietary supplements and other	Kava (Piper methysticum), Ashwagandha	
preparations affecting sleep-wake	(Withania somnifera), Valerian (Valeriana	
regulation	officinalis), St. Johns Wort (Hypericum	
	Perforatum)	
OTC stimulants		
Diet aids		
Melatonin	]	

Psychoactive medications, medications associated with drowsiness/sedation and stimulants will not be allowed because they could interfere with study outcomes. These include prescription, over-the-counter and dietary/herbal supplements. The use of such medications must be discontinued for 2 weeks prior to Visit 1. Participants who develop a cold or flu during the work week use of the device should contact the study team immediately to discuss medication usage. The Investigator will make all final decisions regarding exclusion of participants on the basis of medication.

Before enrolling a woman of child-bearing potential in this clinical study, Investigators must review the following information with the participant:

- Risk of pregnancy;
- Contraceptives in current use;
- Drug interactions with hormonal contraceptives; and
- Pregnancy prevention during the study.

All women of child bearing potential, (defined as any woman, unless surgically sterile or postmenopausal for at least 1 year) must be instructed to contact the Investigator immediately if they suspect they might be pregnant while participating in this study. If a participant becomes pregnant, she will be discontinued from the study

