# Daytime Visit 1 Procedures (Up to 2 hours):

# Initial evaluation and anthropometric measurements:

Participants will be asked to report to the office for a daytime visit. After a full explanation of the consent and after all the participants' questions have been answered, they will be asked to sign the consent form. A detailed interview will be performed verifying eligibility criteria, and review of work and non-work schedules.

Participants will be asked to fill out the following baseline questionnaires:

- Medical History Questionnaire and Review of Systems
- Epworth Sleepiness Scale
- Insomnia Severity Questionnaire
- Cambridge-Hopkins Questionnaire (RLS screening)
- STOP-BANG Questionnaire
- Questions about sleep schedule and sleep quality.

Participants will have their height, weight, neck circumference, temperature, respiratory rate and blood pressure including heart rate (heart rate, systolic and diastolic after being seated for approximately 5 minutes) recorded.

Participants will be trained on the use of the sleep logs and actigraphy including instructions from the study staff on how to wear the actigraph. Participants will be asked to keep a sleep log and wear an actigraph during the entire course of the study. It is important participants keep to their regular sleep schedule throughout the study.

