### **Adverse Event Reporting Period**

Adverse events, both serious and non-serious, are to be recorded on the Adverse Events Case Report Form provided by the Sponsor from the time of the participant's informed consent signature until the end of the participant's study participation. If the participant reports or the Investigator learns of a new AE(s) up to 7 days after the participant's last study visit or a new SAE(s) up to 30 days after the participant's last study visit, the event needs to be recorded on the form provided by the Sponsor. All SAEs should be reported to the Sponsor within 24 hours of occurrence. All device deficiencies, use or user errors, and equipment failures will be documented. Use or User errors will be captured as part of the source documentation. Device deficiencies and equipment failures will be kept on a separate log. The serial numbers and type of deficiency/failure will be captured. Philips Respironics Engineering team will be notified to troubleshoot any issues associated with the PowerSleep Device.

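### The two-week medication rule is worded as a stop before consent, and for sleep medication and stimulants it is shorter than the past-month exclusion; reword it as a history condition

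*Combined protocol and SAP*

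**What the plan says.** All references are to the combined protocol and SAP.

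- **Concomitant Medications, scope.** After a table of disallowed classes, the text says: "Psychoactive medications, medications associated with drowsiness/sedation and stimulants will not be allowed because they could interfere with study outcomes". It adds: "These include prescription, over-the-counter and dietary/herbal supplements".
- **Concomitant Medications, timing.** The next sentence is: "The use of such medications must be discontinued for 2 weeks prior to Visit 1". The section also gives the Investigator the last word on medication exclusions.
- **Exclusion Criteria.** One bullet excludes "Current use or use of within the past month of a prescription or over-the-counter sleep medication or stimulant; use of psychoactive medication". It ends with "Refer to table below for examples", which points to the same table. The bullet does not say from which date the month is counted. The part on psychoactive medication, after the semicolon, has no interval of its own.
- **Study Procedures and Measurements.** Before Visit 1 the only contact described is an optional telephone pre-screen, by the site or a market research firm. People who meet all the criteria are then invited to Visit 1.
- **Daytime Visit 1 Procedures.** Consent takes place here: "After a full explanation of the consent and after all the participants' questions have been answered, they will be asked to sign the consent form". No earlier consent step is described.

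**The concern.** There are two problems with one sentence.

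The first is its form. It is an instruction to discontinue, it expressly reaches prescription drugs, and it applies to the two weeks that end at the visit where consent is signed. The table lists anxiolytics, sedating antidepressants and opioid analgesics. A person should not stop a prescribed drug of this kind for a study that they have not yet agreed to join. The protocol protects some other treatments: stable therapy for hypertension, dyslipidemia or thyroid replacement is to continue unchanged. Nothing similar is said for the drugs in the table.

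The second is its interval. For sleep medication and stimulants, a reader who consults only the medication section finds two weeks, while the Exclusion Criteria say a month. A telephone screener who works from the medication section could give a caller the wrong interval.

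**Working it through.** There is no stated figure to reproduce. The check compares the texts, with one subtraction.

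**Step 1: order of events.**

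| Event | Timing | Source |
|---|---|---|
| Medication to be stopped | The 14 days before Visit 1 | Concomitant Medications |
| Telephone pre-screen, if done | Before Visit 1 | Study Procedures and Measurements |
| Consent explained and signed | At Visit 1 | Daytime Visit 1 Procedures |

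As worded, all 14 days come before consent.

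**Step 2: directive or history condition?** The verb is one of stopping. Elsewhere the protocol does word a history condition clearly: the smoking exclusion admits people who have already been free of nicotine for 30 days. The medication sentence does not take that form. On the other side, only people who already meet the criteria are invited to Visit 1, and no section describes anyone being told to stop a drug. The look-back reading is the more likely intention, but the words do not say it.

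**Step 3: the two intervals.** Let M be the length of a month (28 to 31 days) and d the number of days from Visit 1 to the date from which the month is counted. The two-week rule reaches back 14 days from Visit 1, which is 14 + d days from that date. The gap is M − 14 − d.

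- Month counted from Visit 1 (d = 0): 28 − 14 = 14 days, to 31 − 14 = 17 days.
- Month counted from a Daytime Visit 2 that falls 14 to 16 days after Visit 1 (the late end of its window): from 28 − 14 − 16 = −2 days to 31 − 14 − 14 = 3 days. Here the two rules nearly coincide.

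The documents choose neither date, so the size of the mismatch depends on an anchor that is not stated.

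**Step 4: what happens to a person in the gap.** Suppose that the last dose of zolpidem or modafinil was 20 days before Visit 1, and that the month is counted from Visit 1. Since 20 > 14, the two-week rule is met. Since 20 < 28, the past-month exclusion applies. A participant has to pass every criterion, so this person is excluded. The rules give one answer if both are read, and the two-week rule has no separate effect for these drugs.

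**Step 5: the other listed drugs.** If the month attaches only to sleep medication and stimulants, as the semicolon suggests, two weeks is the only interval stated for the remaining classes. A two-week look-back for them can stand beside the month without contradiction.

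**The case against.** The strongest reply is that nobody would be told to stop anything. Current users of sleep medication, stimulants or psychoactive drugs are excluded outright, only people who already qualify are invited, and the Investigator decides doubtful cases. Most of this stands, and it is why actual exposure may be nil. It does not defend the wording: the Investigator's authority neither picks an interval nor says that a drug should not be stopped in order to join.

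It can also be said that the consent form and telephone script were not available for this review, so an earlier consent for screening cannot be ruled out. That is correct. The protocol text describes signing only at Visit 1.

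Three stronger readings are tempting and are not supported:

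- **That the two intervals lead to wrong enrolment.** Step 4 shows that the stricter rule governs.
- **That harm from a stop before consent would escape adverse event recording, as a separate defect.** The Adverse Events section ties an event to use of the study device, and none has been used before Visit 1. Recording from consent onward is not a fault.
- **That the problem can be sized by counting table classes.** Whether a class is mainly prescription, or counts as sleep medication or a stimulant, is the reader's own sorting. Some rows are mixed, such as the one for attention deficit medicines.

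**Conclusion.** The point holds as a wording fault with a participant-protection side. Read literally, the sentence is a study-driven stop of medication, prescription drugs included, in the 14 days before consent. For sleep medication and stimulants its interval is misleading beside the past-month exclusion, by 14 to 17 days if the month is counted from Visit 1 and by almost nothing if it is counted from a late Visit 2.

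This rests on two assumptions: that consent is not taken before Visit 1, and that the past-month limit covers sleep medication and stimulants but not the psychoactive drugs named after the semicolon. If the month was meant to cover the whole bullet, the two-week figure is misleading for psychoactive drugs as well. The number of people affected cannot be derived from the documents. There is no consequence for power, type I error or the analysis.

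**What to change.** Replace the sentence in Concomitant Medications with a history condition that keeps the existing intervals, for example: *Participants must not have used sleep medication or stimulants in the month before Visit 1, or any other listed class in the 2 weeks before Visit 1; no one should stop a prescribed medication in order to qualify.* In the Exclusion Criteria, state that the month is counted back from Visit 1. If the sponsor meant the month to cover psychoactive drugs too, both places should say so.

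A single one-month limit for every class would be simpler to state. It would, however, newly exclude people who took a decongestant, cough product or diet aid a few weeks earlier. Keeping both intervals avoids that.

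The cost is one sentence and one added anchor date, and possibly a few more screen failures among people who would otherwise have stopped a drug to join. That number cannot be estimated from the documents. Visits, windows, sample size and analysis stay as they are.
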